#### **Expectedness of adverse events**

Expectedness will be assessed by the sponsor.

An unexpected adverse event is one where the nature or intensity is not consistent with the information in the neridronic acid investigator's brochure.

Furthermore, reports that add significant information about the specificity or severity of a known, already documented adverse reaction constitute unexpected adverse events. For example, an adverse event more specific or more severe than expected would be considered "unexpected".

---

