### **Notification of serious adverse reactions**

All suspected adverse drug reactions related to an IMP (the tested drugs and comparators) that occur in this trial, and that are both unexpected and serious are subject to expedited reporting.

Once a year throughout the clinical trial, the sponsor will provide the member states in whose territory the clinical trial is being conducted and the IECs with a listing of all suspected unexpected serious adverse reactions which have occurred over this period and a report of the subjects' safety.

In addition, the sponsor will ensure that all reportable events are reported in compliance with applicable international and national regulatory requirements.

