### 15.1 Adverse events

All adverse events with start date/time after first IMP administration in a subject administered a trial treatment will be defined as treatment emergent adverse events (TEAE) irrespective of causal relationship.

A pre-treatment non-TEAEs is an adverse event starting in the pre-treatment period as defined in Section 8.2.2.

If there are partial dates or times, an adverse event will be considered treatment emergent unless the information available will clearly exclude it. Further details can be found in Section 20.1.6.1.

The causal relationship of TEAEs to IMP is categorized as follows:

Category	Assessment by investigator:
Related	certain probable/likely possible
Not related	unlikely not related
Unknown	unassessable/unclassifiable conditional/unclassified causal relationship is missing

A TEAE is considered to be ‘expected’ when the nature or intensity is consistent with the information in the neridronic acid investigator’s brochure. Otherwise, it is considered to be an ‘unexpected’ TEAE. Expectedness will be assessed by the sponsor.

The following overview tables will be generated overall, i.e., for the single treatment group neridronic acid 400 mg.

1. Summary of the number and percentage of subjects with at least 1:

- TEAE.
- Serious TEAE.
- Non-serious TEAE.
- Unexpected TEAE.
- Related TEAE.
- Related serious TEAEs.
- TEAE leading to discontinuation from IMP.
- TEAE leading to discontinuation from the trial.
- Deaths.

The percentage denominator will be the number of subjects.

2. Summary presenting the number of TEAEs per subject categorized as 0, 1, 2, 3, 4, 5, and >5.
3. Summary of the number and percentage of TEAEs for:
  - TEAEs.
  - Serious TEAEs.
  - Non-serious TEAEs.
  - Unexpected TEAE.
  - Related TEAEs.
  - Related serious TEAEs.
  - TEAE leading to discontinuation from IMP.
  - TEAE leading to discontinuation from the trial.

The percentage denominator will be the total number of TEAEs.

If more than 10 subjects discontinue the trial/IMP due to TEAE, the incidence and the incidence rate of TEAEs leading to discontinuation from the trial/from IMP will be summarized by SOC and PT.

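### SAP 15.1 defines an expected TEAE by the wrong complement of the protocol's rule for unexpected events, so the stated definition is too wide

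*SAP*

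**What the plan says.** Protocol section 12.3.1, under the expectedness of adverse events, defines the unexpected event: "An unexpected adverse event is one where the nature or intensity is not consistent with the information in the neridronic acid" investigator's brochure. It then treats reports that add significant information on the specificity or severity of an already documented reaction as unexpected, and gives the example that "an adverse event more specific or more severe than expected would be considered" unexpected.

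SAP section 15.1 starts from the other side and defines the expected event. A TEAE is expected "when the nature or intensity is consistent with the information in the neridronic acid" investigator's brochure. The next sentence handles everything else: "Otherwise, it is considered to be an" unexpected TEAE. Then follows "Expectedness will be assessed by the sponsor", a statement that the protocol also makes.

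The classification feeds an Unexpected TEAE row in two overview tables of SAP 15.1, one counting subjects and one counting events. Protocol section 14.1.6.1 promises a TEAE summary by expectedness, but the TEAE descriptors listed in SAP 15.1.1 do not include it. These two rows are therefore the only tabulation by expectedness that the SAP specifies.

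SAP section 7.1, which lists changes from the protocol, names only the definitions of the Full Analysis Set and the Pharmacodynamic Set. The amendment rationale in SAP 7.3 does not mention expectedness either.

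**The concern.** When a condition built with *or* is turned into its opposite, the *or* has to become *and*. The SAP moved the negation but kept the *or*. As a result, its expected category admits an event that matches the brochure on one attribute only. A listed reaction at greater severity than described matches on nature, so the SAP sentence makes it expected. The protocol singles out that same case as unexpected.

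The trial's primary objective is safety and tolerability. A known reaction occurring at more than its described intensity is tolerability information that the unexpected category exists to show. SAP section 3 says that the document contains all definitions for the analysis and that a contract research organization will analyse the trial in accordance with it. Its wording is therefore what programmers and readers of the tables will rely on.

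**Working it through.** The plan gives no figure here, so the check is one of logic.

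**Inputs.** Let N mean that the nature is consistent with the brochure, and I that the intensity is consistent with it.

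- Protocol 12.3.1: unexpected = (not N) or (not I). Hence expected = N and I.
- SAP 15.1: expected = N or I. Its residual clause gives unexpected = not (N or I) = (not N) and (not I).

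**All four combinations.**

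| Nature consistent | Intensity consistent | Protocol 12.3.1 | SAP 15.1 | Agree? |
|---|---|---|---|---|
| yes | yes | expected | expected | yes |
| yes | no | unexpected | expected | no |
| no | yes | unexpected | expected | no |
| no | no | unexpected | unexpected | yes |

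The protocol calls 1 of 4 combinations expected and the SAP calls 3 of 4 expected. They disagree in 3 − 1 = 2 combinations.

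**Direction.** Every event that is unexpected under the SAP (neither attribute consistent) is also unexpected under the protocol (at least one not consistent), but not the reverse. For any set of data, the SAP count of unexpected TEAEs is therefore equal to or lower than the protocol count. It cannot be higher.

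**Which disagreement matters.** The second row is the listed reaction of greater severity. The third row is close to empty in practice, because an event whose nature is not in the brochure has no described intensity with which to be consistent.

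**After correction.** If expected is redefined as N and I, its complement is (not N) or (not I), and the two documents agree in 4 of 4 combinations.

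**The case against.** The strongest reply is that no one will run this truth table. Both documents give the assessment of expectedness to the sponsor. The adverse event derivation rules in SAP 20.1.6.1 cover dates, TEAE status, deaths, onset, duration and the ordering of causality, but contain no algorithm for expectedness. The adverse event fields listed in Protocol 12.3.1 record intensity but no item on consistency with the brochure. The SAP also declares itself to be in accordance with protocol version 5.0. A sponsor that applies the protocol's definition would deliver a correct flag, and the tables would be right despite the sentence.

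This stands in part. A reader might infer that the unexpected counts will certainly be wrong, and the documents do not support that. The reply does not rescue the sentence, however. The SAP places its own rule directly before the statement that the sponsor assesses expectedness, and does not refer to the protocol's definition. Even if the counts are right, the SAP then carries a definition that does not describe them.

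The second reply concerns reach, and it stands. The primary endpoint is the occurrence of any TEAE, whatever its expectedness. No inferential testing is planned. Intensity is tabulated by System Organ Class and Preferred Term, serious TEAEs have their own tables, and acute phase events have a listing and a summary by Preferred Term. Severe events remain visible elsewhere in the report.

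Three further inferences are tempting, and the documents support none of them:

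- *That expedited reporting is compromised, or that the SAP rows should reconcile with the expedited cases.* Expedited reporting covers suspected drug reactions "that are both unexpected and serious are subject to expedited reporting". It is set by the protocol alone. The SAP rows cover TEAEs of any seriousness and any causality, so the two counts would differ even with the sentence corrected.
- *That 1 against 3 of 4 combinations measures the size of the error.* It counts logical cases, not events.
- *That fever and flu-like reactions will be the main source.* Protocol 6.3 says that they predominate among drug-related events. The severity that the brochure describes for them is not in the documents.

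**Conclusion.** The SAP sentence is wrong as written: it states the wrong complement of the protocol's rule, the difference is not declared, and nothing else in the documents corrects it.

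What follows depends on how the flag is assigned. If it follows the SAP sentence, listed reactions of greater severity than described are counted as expected, and both Unexpected TEAE rows are too low whenever such events occur. If it follows Protocol 12.3.1, the counts are correct and the fault is confined to the definition printed in the SAP. The documents do not settle which of the two applies. The number of events cannot be given either, since it depends on trial data and on an investigator's brochure that is not among the documents.

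This is a definite textual error in a safety definition, with a bounded effect on two descriptive rows. It should be corrected, but it does not threaten the trial's conclusions.

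**What to change.** In SAP 15.1, define a TEAE as expected when its nature and intensity are both consistent with the investigator's brochure. Add that the tabulated flag is the sponsor's assessment under Protocol 12.3.1, including that section's rule on events that are more specific or more severe. The residual clause for unexpected TEAEs can then stay as it is.

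The cost is a short rewording of one definition in the SAP. It needs no new data and no change in trial conduct. If flags have been set by the present sentence, they would have to be reviewed, and the unexpected count could rise or stay the same but not fall.

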#### **9.3.1 Subject discontinuation from the trial**

All bisphosphonates have a long retention time in bone, and duration of efficacy is related to their persistent effects on bone turnover, specifically the inhibition of activation of bone resorption (Al Nofal et al. 2015; Naylor and Eastell 2012; Jung and Lein 2014). Collection of follow-up data is important for characterizing the safety and efficacy of neridronic acid. Subjects who receive any treatment, even a partial infusion, should be encouraged to remain in the trial for the full duration for follow-up safety and efficacy assessments.

Under certain situations, discontinuation from the trial may be required or be in the best interest of the subject from a risk/benefit perspective. Table 1 lists mandatory and optional reasons for discontinuation from the trial.

Table 1: Reasons for compulsory and optional discontinuation of subjects

Reason	Discontinuation from trial	
	Compulsory	Optional
Enrollment failure (i.e., subject was not allocated to treatment due to failure to meet inclusion or exclusion criteria and did not receive IMP).	X	
Subject withdrawal of consent (the reason for withdrawal must be specified).	X	
Subject death.	X	
Subject loss to follow-up (i.e., no further contact with the subject is possible).	X	
Sponsor decision to discontinue the subject.	X	
Technical reasons (e.g., site is no longer able to function or participate in the trial, and the subject is too remote from other site locations).		X
Sponsor decision to terminate the trial.	X	
Other reasons (e.g., subject becomes engaged in litigation related to their disability from CRPS in which monetary gain may affect their objective participation in the trial).		X

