## 5 TRIAL DESIGN

### 5.1 Overall trial design and plan

Only a brief synopsis of the trial design is presented here; full details can be found in the trial protocol.

This is a multi-site, open-label, single-arm, Phase III safety trial of intravenous neridronic acid in subjects with CRPS.

There will be an enrollment period lasting up to 60 days, a treatment period consisting of 4 infusions over 10 days, and a follow-up period of approximately 50 weeks (Visit 6 [Week 2] through Visit 11 [Week 52]). The subjects are expected to be in the trial for approximately 60 weeks (14 months). See [Figure 1](#) for a summary of the trial as a flow diagram. For details, refer to the schedule of events defined in the trial protocol.

[figure not shown]

Figure 1: Flow diagram summary of the trial

The investigational medicinal product (IMP) is 100 mg neridronic acid diluted in 500 mL normal saline and administered by slow intravenous infusion (240 minutes [maximum 260 minutes]) at Visit 2, Visit 3, Visit 4, and Visit 5, resulting in a total dose of 400 mg neridronic acid.

In addition to the assessments applicable to all trial subjects, bone biopsies will be performed in a subset of trial subjects to assess the bone safety of neridronic acid 400 mg. In addition, bone imaging assessments (bone densitometry and magnetic resonance imaging) will be performed in a subset of trial subjects. Bone biopsies and bone imaging data will only be obtained from subjects participating at sites in the United States of America (USA).

An external independent data monitoring committee (DMC) will periodically review safety information from the trial and monitor trial conduct and overall progress.

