### 5.2 Sample size

The sample size is intended to maximize available safety data to support product registration. In combination with subjects receiving active treatment in the ongoing placebo-controlled trial (KF7013-01) and further planned trials of neridronic acid, the number of subjects included in this trial is intended to support regulatory requirements for at least 500 subjects on neridronic acid evaluated for safety. It is estimated that approximately 290 subjects will be included in this trial.

For bone biopsies, results from 15 evaluable biopsy specimens are considered adequate to be able to identify qualitative bone abnormalities such as osteomalacia as well as quantitative indicators of impaired mineralization.

For bone densitometry and magnetic resonance imaging (MRI) assessments, results from 30 subjects are considered sufficient to demonstrate feasibility and support a rationale for the future use of these assessments in trials of neridronic acid in CRPS.

If the expected number of bone biopsies or bone densitometry and MRI assessments are not obtained, it is not planned to increase the number of subjects included in the trial.

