## 8 ANALYSIS CONVENTIONS

### 8.1 General principles

If 2 or more of the population sets as defined in the SAP coincide, presentations will only be prepared for 1 population.

All presentations will be done overall, i.e., for the single treatment group neridronic acid 400 mg. The data collected and derived in the trial will be presented in subject data listings.

Data collected in this trial will be summarized according to their nature as follows:

- Continuous variables: number of non-missing observations, arithmetic mean, standard deviation, minimum and maximum values, median and quartiles. If there are less than 5 observations, descriptive statistics will be presented based on the rules specified in Section 20.1.1.2.
- Categorical variables: absolute and relative frequencies. If not defined otherwise, the percentage denominator will be the number of subjects still in the trial at the respective time point in the analyzed population.
- Time-to-event variables: number of subjects, number of subjects with event, number of censored subjects, first quartile, median, and third quartile including 95% confidence interval. For calculating the survival estimate confidence interval (CI) bounds, the log-log transformed estimate of CI bounds will be used. In addition, Kaplan-Meier estimates and plots will be provided with the respective number at risk and the Kaplan-Meier estimates at the relevant time points together with the median and its 95% CI. Censoring mechanisms will be described in the respective section.

Medical terms (e.g., prior and concomitant diseases, adverse events) will be coded via Medical Dictionary for Regulatory Activities (MedDRA), and medications will be coded according to World Health Organization Drug Dictionary (WHO-DD).

[Table 1](#) shows the use of analysis sets in different analyses as defined in Section 9.

Table 1: Use of analysis sets

	Enrolled Set	Allocated Set	SAF	FAS	TCS	PD Set
Subject disposition	X					
Discontinuations		X				
Protocol deviations			X			
Demographics			X			
Other baseline characteristics			X			
Subject medical history			X			
Previous and concomitant medication			X			
Exposure			X			
Compliance			X			
Primary safety endpoint			X			
Secondary safety endpoint			X			
Secondary efficacy endpoints				X	X	
Adverse events			X			
Laboratory values			X			
Vital signs			X			
Twelve-lead ECG			X			
Physical examination			X			
Bone turnover markers						X
Health economics data				X		

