If more than 5% of the subjects discontinue the trial due to TEAE, the distribution of the time to discontinuation from trial due to TEAE will be summarized using time-to-event methods. Time will be days until discontinuation. The time to discontinuation will be censored at the End-of-Trial Visit or at the time point of discontinuation if not due to TEAE.

If more than 5% of the subjects permanently discontinue IMP due to TEAE, the distribution of the time to discontinuation from IMP due to TEAE will be summarized using time-to-event methods. Time will be days until discontinuation. The time to discontinuation will be censored at the last planned infusion visit (Visit 5), or at the time point of discontinuation, whichever occurs first.

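### The Kaplan-Meier curve for trial discontinuation due to a TEAE censors exits that preclude the event, so it can overstate, and never understates, the proportion who leave for a TEAE

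*SAP*

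**What the plan says.** SAP 15.1 plans a time-to-event summary of trial discontinuation due to a TEAE. It is conditional: "If more than 5% of the subjects discontinue the trial due to TEAE". Its censoring rule is: "The time to discontinuation will be censored at the End-of-Trial Visit or at the time point of discontinuation if not due to TEAE".

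SAP 8.1 sets the output for every time-to-event variable: event and censoring counts, quartiles with confidence intervals, and, in its words, "Kaplan-Meier estimates and plots will be provided with the respective number at risk", with estimates at the relevant time points. Neither document mentions competing risks or a cumulative incidence function.

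The other ways out of the trial are in Table 1 of Protocol 9.3.1. They include withdrawal of consent, "Subject loss to follow-up", sponsor decisions, technical reasons such as a site that can no longer take part, and other reasons.

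The same event is also counted directly. One of the SAP 15.1 overview tables is a "Summary of the number and percentage of subjects with at least 1" event of each listed type, and TEAE leading to discontinuation from the trial is one of those types. For that table, "The percentage denominator will be the number of subjects".

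**The concern.** The event here is itself a kind of exit. A subject who has already left for another reason cannot later leave because of a TEAE, so the other exit does not hide the event but rules it out. Censoring such subjects lets Kaplan-Meier treat them as still able to leave for a TEAE at the same rate as those who remain. The resulting 1-KM describes a hypothetical trial in which nobody leaves for any other reason.

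Time to onset of a TEAE (SAP 15.1.1) is different. A subject can still have a TEAE, unobserved, after leaving, so the argument here does not carry over to that analysis.

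At stake is a tolerability curve in a safety trial. The report could show two different Week 52 figures for one event, a crude percentage and a larger 1-KM, with nothing to explain the gap.

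**Working it through.** **Inputs from the documents.** SAP 5.2: "It is estimated that approximately 290 subjects will be included in this trial". Trigger: 0.05 × 290 = 14.5, so at least 15 subjects, and 15/290 = 5.17%. Follow-up runs to Visit 11 at Week 52 (SAP 5.1).

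**Assumptions.** Let *a* be the proportion leaving for a TEAE by Week 52 and *b* the proportion leaving for other reasons. The documents give neither, so both are varied: *a* = 5.17% and 10%; *b* = 5% to 30%. The plan has no figure of its own to reproduce, because 290 rests on no event or dropout rate.

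**Direction.** At each TEAE exit, Kaplan-Meier adds (its own survival estimate) ÷ (number at risk). Aalen-Johansen adds (proportion still in the trial) ÷ (the same number at risk). The proportion still in the trial also falls at other exits, so it is never larger than the Kaplan-Meier survival. Hence 1-KM is at least the cumulative incidence, and is larger once any other exit precedes a TEAE exit.

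**Size with evenly spread exits.** With constant cause-specific hazards the total cumulative hazard is H = -ln(1 - a - b), and the TEAE part is H1 = H × a/(a + b). Then 1-KM = 1 - exp(-H1), while the cumulative incidence is *a*.

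Example with a = 0.10, b = 0.20: H = -ln(0.70) = 0.3567; H1 = 0.3567 × 0.10/0.30 = 0.1189; 1-KM = 1 - exp(-0.1189) = 11.2%, against 10.0%.

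| Other exits | 1-KM when a = 5.17% | Excess (points) | 1-KM when a = 10% | Excess (points) |
|---|---|---|---|---|
| 5% | 5.31% | 0.14 | 10.27% | 0.27 |
| 10% | 5.46% | 0.28 | 10.56% | 0.56 |
| 20% | 5.78% | 0.61 | 11.21% | 1.21 |
| 30% | 6.18% | 1.00 | 11.99% | 1.99 |

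Product-limit and Aalen-Johansen estimates on 290 simulated subjects with uniform exit times (300 draws per case) agree with the table to within 0.03 points. Aalen-Johansen equals the crude percentage in every case, because every simulated subject either exits or reaches Week 52.

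**Sensitivity to timing** (15 or 29 TEAE exits, up to 87 other exits, i.e. 30%):

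- All TEAE exits in days 1-30, other exits evenly spread: the excess is at most 0.06 points with 15 TEAE exits and 0.13 with 29.
- All TEAE exits before any other exit: the excess is zero.
- All 87 other exits before any TEAE exit: 290 - 87 = 203 remain at risk, so 1-KM is 15/203 = 7.39% against 5.17%, or 29/203 = 14.29% against 10.00%. The ratio is 290/203 = 1.43.

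**Against sampling error.** The standard error of the crude proportion is √(0.0517 × 0.9483/290) = 1.3 points, or √(0.10 × 0.90/290) = 1.8 points. With 20% other exits, evenly spread, the excess of 0.6 or 1.2 points is roughly half to two thirds of one standard error.

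**The case against.** **The analysis may never run.** It needs at least 15 of 290 subjects to leave the trial, not just the infusions, because of a TEAE. Protocol 9.3.2 says that subjects taken off IMP should stay in the trial unless a Table 1 reason applies, and Table 1 has no adverse-event row. This stands, and it limits how much the point matters. It does not remove it: Protocol 12.3.1 still allows trial discontinuation because of an adverse event, and the SAP plans the output.

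**The right overall figure is already planned.** A reader might infer that the trial's reported loss due to TEAEs will be inflated. The documents do not support that. The 15.1 overview percentage uses all subjects as its denominator and is untouched by the censoring rule, and SAP 10.2 tabulates the reasons for discontinuation. At event proportions of 5-10% the quartiles and median are unlikely to be reached either, so only the curve and its time-point estimates are exposed.

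**The bias may be negligible.** A reader might also infer that the curve always overstates. It need not. All dosing falls within the first 10 days (21 at most), and Protocol 6.3 and 8.2 describe mainly acute-phase symptoms after the first administration. If TEAE exits cluster there, the excess is near zero. The accurate statement is that the curve never understates.

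**Kaplan-Meier with other exits censored is a recognised cause-specific summary.** That is true, and the SAP does not call 1-KM the proportion who leave. But nothing in the plan warns the reader against taking it that way.

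**Not every other exit is a competing event.** It is tempting to count all of them. Sponsor termination of the trial or closure of a site merely cuts off observation, and censoring is right for those.

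**Conclusion.** The point holds as a minor one. The stated censoring rule, combined with Kaplan-Meier, targets the wrong quantity for an event that other exits preclude. Under the assumption of evenly spread exits, with TEAE loss of 5-10% and other loss of 5-30%, the excess is about 0.1 to 2 percentage points. It runs from zero when TEAE exits come first to 4.3 points in the extreme case where 30% leave for other reasons before any of 10% leave for a TEAE. All of these rest on assumed dropout, since the documents state none.

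The output is conditional and descriptive, Protocol 14.1.2 plans no inferential testing, and no decision rule uses the curve. The primary endpoint and the crude percentages are not affected.

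**What to change.** In SAP 15.1, for time to trial discontinuation due to a TEAE:

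- Report the Aalen-Johansen cumulative incidence function with confidence intervals in place of Kaplan-Meier.
- Treat subject-level discontinuation for other reasons, such as withdrawal of consent or loss to follow-up, as a competing event.
- Censor at Visit 11 or at administrative end of follow-up, such as sponsor termination of the trial or site closure.
- State which eCRF discontinuation reasons fall into each class. Where there is administrative censoring, note that the Week 52 estimate need not equal the crude percentage.

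Add the matching exception to SAP 8.1. Keep Kaplan-Meier for all-cause trial discontinuation in SAP 10.2, where no exit competes with the event.

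The cost is a few lines of SAP text and a small programming change. The reasons for discontinuation are already taken from the eCRF (SAP 20.1.2.1), so no new data are needed. If the sponsor prefers to keep Kaplan-Meier here, the minimum is a footnote saying that the curve is cause-specific and does not estimate the proportion who leave because of a TEAE.

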Pooling of sites	
Individual sites will be combined to achieve pooled sites of similar size and with a sufficient number of subjects. Sites will be pooled by geographical region. The majority of sites are located in the United States of America (USA). Sites in the USA will be pooled in 4 regions based on United States (US) states:
 
 
• US North East: Connecticut (CT), Delaware (DE), Illinois (IL), Indiana (IN), Maine (ME), Maryland (MD), Massachusetts (MA), Michigan (MI), New Hampshire (NH), New Jersey (NJ), New York (NY), Ohio (OH), Pennsylvania (PA), Rhode Island (RI), Vermont (VT), and Washington D.C. (DC).
 
• US South East: Alabama (AL), Florida (FL), Georgia (GA), Kentucky (KY), North Carolina (NC), South Carolina (SC), Tennessee (TN), Virginia (VA), and West Virginia (WV).
 
• US Midwest: Arkansas (AR), Colorado (CO), Iowa (IA), Kansas (KS), Louisiana (LA), Minnesota (MN), Mississippi (MS), Missouri (MO), Montana (MT), Nebraska (NE), New Mexico (NM), North Dakota (ND), Oklahoma (OK), South Dakota (SD), Texas (TX), Wisconsin (WI), and Wyoming (WY).
 
• US West: Alaska (AK), Arizona (AZ), California (CA), Hawaii (HI), Idaho (ID), Nevada (NV), Oregon (OR), Utah (UT), and Washington (WA).
 
 
The sites in Europe will be pooled in one region, European Union (EU).

Pre-treatment-period	Before first IMP administration (excluded), i.e., the period between signature of the informed consent form and first administration of IMP.

Term	Definition
Subjects discontinued from treatment	Subjects permanently discontinued from IMP, i.e., subjects who stopped treatment prior to, or at any time during Visit 2, 3, 4, or 5.
Treated subjects	Subjects with at least 1 administration of IMP, including partial infusions.
Treatment period	The treatment period includes the four infusion visits starting at Visit 2 up to Visit 5. If a subject is permanently discontinued from treatment, the treatment period ends at the visit of the last infusion.
Treatment completers	Treated subjects who completed IMP administration according to the protocol, i.e., subjects who received the full dose of all 4 planned infusions of IMP. Treatment completers form the Treatment Completers Set defined below.
Trial completers	All subjects completing Visit 11 according to the protocol.

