## 10.2 Subject discontinuations

Discontinuations from the trial and from IMP will be presented for allocated subjects overall, and per country.

Reasons for discontinuations from the trial and from IMP will be presented for:

- Subjects allocated and discontinued from the trial
- Subjects allocated and discontinued IMP intake.
- Subjects allocated and discontinued from the trial per trial phase, i.e., during the treatment period, and during the follow-up period

Percentage denominator will be the number of subjects discontinuing.

The details for “other reasons” will be presented in a listing, if applicable.

If more than 10% of the allocated subjects discontinue the trial/IMP the distribution of the time to discontinuation from trial/IMP will be summarized using time-to-event methods. Time will be days until discontinuation. The time to discontinuation from the trial will be censored at the subject’s last planned visit, i.e., Visit 11. The time to discontinuation from IMP will be censored at the last planned infusion visit (Visit 5) or at the early termination visit in case of premature discontinuation from the trial, whichever occurs first.

All data will be presented in a subject data listing sorted by site.

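### Two conditional censoring rules for time to IMP discontinuation (SAP 15.1 and 10.2) can censor the events they are meant to count

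*SAP*

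**What the plan says.** **IMP discontinuation due to a TEAE (SAP 15.1).** The summary is triggered by the condition "If more than 5% of the subjects permanently discontinue IMP due to TEAE". Subjects are censored at the last planned infusion visit (Visit 5), "or at the time point of discontinuation, whichever occurs first". No cause of discontinuation is named. The paragraph directly above, on leaving the trial because of a TEAE, says "censored at the End-of-Trial Visit or at the time point of discontinuation if not due to TEAE". The rule for time to onset of a TEAE in SAP 15.1.1 carries the same restriction.

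**IMP discontinuation for any reason (SAP 10.2).** The trigger is "If more than 10% of the allocated subjects discontinue the trial/IMP the distribution of the time to discontinuation from trial/IMP will be summarized". Time to IMP discontinuation is censored at Visit 5 "or at the early termination visit in case of premature discontinuation from the trial, whichever occurs first".

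**Who has discontinued (SAP 8.2.2).** "Subjects permanently discontinued from IMP, i.e., subjects who stopped treatment prior to, or at any time during Visit 2, 3, 4, or 5". There is no exception for subjects who also leave the trial.

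**Other relevant text.** SAP 8.1 leaves the censoring mechanism to the individual sections, and SAP 20.1.1.13 adds nothing for Kaplan-Meier analysis. SAP 8.2.2 ends the treatment period of a permanently discontinued subject at the visit of the last infusion. SAP 20.1.1.11 defines end of treatment as the date of the last IMP administration.

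**The concern.** A censoring rule should apply only to subjects who have not had the event. In SAP 15.1, a subject who stops IMP because of a TEAE discontinues at exactly the time that the rule names for censoring. In SAP 10.2, leaving the trial during the infusion period is handled as loss of follow-up. For this outcome it is not: a subject who has left will receive no further infusion, so the IMP stop has already happened and is known.

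At stake are two supplementary safety curves. They are produced only when discontinuation is fairly common, which is when a reader would look at them. If programmed as written, they could disagree with the crude discontinuation tables in the same report. SAP 3 gives the analysis to a contract research organization working to this SAP, so the wording should not depend on a programmer guessing the intent.

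**Working it through.** The plan states no figure for either analysis, and Protocol 14.1.2 makes all analyses exploratory with no inferential testing, so there is nothing to reproduce. The check sets the rules side by side and then illustrates their size.

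**Inputs.** N = 290 (SAP 5.2, approximate). Triggers: more than 5% for TEAE-related stops (SAP 15.1) and more than 10% for any-reason stops (SAP 10.2). With 290 subjects:

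- 5%: 14/290 = 4.8% and 15/290 = 5.2%, so at least 15 TEAE-related stops.
- 10%: 29/290 = 10.0% and 30/290 = 10.3%, so at least 30 stops.

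**TEAE-related rule.**

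| Rule | Censoring on discontinuation |
|---|---|
| Leaving the trial due to TEAE (15.1) | only if not due to a TEAE |
| Time to onset of TEAE (15.1.1) | only if not due to a TEAE |
| IMP discontinuation due to TEAE (15.1) | any discontinuation |

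Read literally, the third rule gives 0 events and a 0% curve, in an analysis that runs only when at least 15 subjects had the event. With the restriction restored, 15 TEAE stops and no other stops give 15/290 = 5.2%.

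**Any-reason rule.** Because the earlier date applies, the early-termination clause matters only for subjects who leave before Visit 5. Every such subject has permanently stopped IMP under SAP 8.2.2. The clause therefore has two possible effects:

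- If the IMP stop is dated at the departure, the clause censors an event.
- If the stop is dated earlier, for example at the last infusion, the event comes first and the clause does nothing.

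**Illustration.** The product-limit estimate is 1 − Π(1 − d/n), where d is the number of events and n the number at risk on each day. Assumptions: 30 stops, 10 on each of Days 1, 4 and 7; everyone else is censored on Day 10; leavers are censored on the day they stop. The number at risk is then 290, 280 and 270.

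| Of 30 stops, by leaving | Events on Days 1, 4, 7 | Calculation | Estimate |
|---|---|---|---|
| 0 (or all counted) | 10, 10, 10 | 1 − (280/290)(270/280)(260/270) | 10.3% |
| 3 | 9, 9, 9 | 1 − (281/290)(271/280)(261/270) | 9.3% |
| 8 | 8, 7, 7 | 1 − (282/290)(273/280)(263/270) = 0.07648 | 7.6% |
| 15 | 5, 5, 5 | 1 − (285/290)(275/280)(265/270) | 5.3% |
| 30 | 0, 0, 0 | no events | 0% |

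The documents give no expected number of stops or leavers, so the table shows a range and is not a forecast.

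**The case against.** **The zero-event reading is unrealistic.** SAP 15.1 names the event and requires more than 5% of subjects to have had it, and SAP 8.1 reports events and censored subjects as separate counts. A sensible programmer would supply the missing restriction or resolve the tie in favor of the event. This is fair: the fault is most likely a dropped phrase, and a flat curve is not the expected output. But the sentence still names the event time as a censoring time, and no other section corrects it.

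**An IMP stop precedes the early termination visit.** SAP 8.2.2 and 20.1.1.11 point to the last infusion as the end of treatment. If the event is dated there, subjects who leave are counted. This stands in part: a subject who stops IMP first and leaves later can be counted at the earlier stop. However, SAP 10.2 does not say how the event is dated, and on this reading the early-termination clause has no function. The argument makes the clause redundant, not correct.

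**Stronger readings that the documents do not support.**

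- A reader might infer that the secondary safety endpoint is wrong. It is not: SAP 15.6 reports it as a number and percentage, and SAP 15.1 separately counts subjects with a TEAE leading to IMP discontinuation. Neither uses censoring.
- A reader might infer that the leavers are numerous or especially informative. SAP 15.1 does tabulate TEAEs leading to trial discontinuation, so some departures may be due to adverse events. But Protocol Table 1 does not list an adverse event among the reasons for leaving the trial, and Protocol 9.3.2 encourages subjects who stop IMP to stay in follow-up. The size of this group is unknown.

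**Conclusion.** Both rules need correction, as a minor point. The rule in SAP 15.1 omits a restriction that its two parallel rules have and, taken literally, leaves no events. The rule in SAP 10.2 can lose one event for each subject whose IMP stop is the departure from the trial. On the assumed 30 stops in 290 subjects, the loss runs from none (10.3%) to complete (0%), depending entirely on the unknown share who stop by leaving and on how the stop is dated.

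The consequence is limited to two descriptive curves, each produced only if its trigger is met. The crude discontinuation counts do not change.

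**What to change.** **SAP 15.1.** In the IMP paragraph, keep Visit 5 and the earlier-date rule, and give the discontinuation clause the wording of the paragraph above: "or at the time point of discontinuation if not due to TEAE".

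**SAP 10.2.** Drop the early-termination clause for IMP discontinuation. Count every permanent IMP stop before completion of the planned infusions as an event, including a stop by leaving the trial. Censor only subjects who complete the infusions, at their last infusion visit.

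State one dating rule for the stop, consistent with SAP 8.2.2 and 20.1.1.11. Simply using the date of leaving the trial would misdate a subject who stops IMP at one visit and leaves some days later. Because SAP 10.2 covers allocated subjects and SAP 8.2.2 includes stops before Visit 2, the rule should also give a date for an allocated subject who never starts an infusion.

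**Cost.** A few sentences of SAP wording, before the tables are programmed. No new data and no change to trial conduct.
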